#### 4.6 Duration of Therapy

Subjects should continue protocol therapy as described until:

- Disease progression (Note: treatment should continue until progression is confirmed by repeat scan approximately 6 weeks later to rule out pseudoprogression based on investigator discretion)
- Inter-current illness prevents further administration of treatment
- Unacceptable adverse event(s)

- Subject decides to withdraw from the study, OR
- General or specific changes in the subject's condition render the subjects unacceptable for further treatment in the judgment of the investigator.

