#### 4.7 Duration of Follow Up

Subjects will be followed for up to 3 years after removal from study treatment for determination of OS. Subjects removed from study treatment for unacceptable AEs will be followed for resolution or stabilization of the adverse event(s). All subjects (including those withdrawn for AEs) should be followed after removal from study treatment as stipulated in the protocol.

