#### 4.8 Removal of Subjects from Protocol Therapy

Subjects will be removed from protocol therapy and the PI notified when any of the criteria listed in section 4.6 apply. The reason for discontinuation of protocol therapy will be documented on the eCRF.

In case a subject decides to prematurely discontinue protocol therapy (“refuses treatment”), the subject should be asked if she or he may still be contacted for further scheduled study assessments. The outcome of that discussion should be documented in both the medical records and in the eCRF.

Excessive subject withdrawals from protocol therapy or from the study can render the study un-interpretable; therefore, unnecessary withdrawal of subjects should be avoided.

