#### 4.9 Study Withdrawal

If a subject decides to withdraw from the study (and not just from protocol therapy) an effort should be made to complete and report study assessments as thoroughly as possible. At the time of withdrawal, the investigator should attempt to establish as completely as possible the reason for the study withdrawal.

- The subject should be asked if they are willing to allow for the abstraction of relevant information from their medical record in order to meet the long term follow up (e.g., survival) objectives outlined in the protocol.
- A complete final evaluation at the time of the subject's study withdrawal should be obtained with an explanation of why the subject is withdrawing from the study.
- If the subject is noncompliant and does not return for an end of study follow up assessment, this should be documented in the eCRF.
- If the reason for removal of a subject from the study is an adverse event, the principal specific event will be recorded on the eCRF.

October 01,,  
2020

Excessive subject withdrawals from protocol therapy or from the study can render the study un-interpretable; therefore, unnecessary withdrawal of subjects should be avoided.

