### 6.7.4 Evaluation of Non-Target Lesions using RECIST 1.1 Criteria

Complete response (CR)—Disappearance of all non-target lesions and normalization of tumor marker levels. All LN must be non-pathological in size (<10mm short axis).

Non-complete response (non-CR)/non-progression (non-PD)—Persistence of one or more non-target lesion(s) or/and maintenance of tumor marker level above the normal limits.

Progressive disease (PD)—Appearance of one or more new lesions and/or unequivocal progression of existing non-target lesions.

**NOTE:** Any progressive disease as defined by RECIST1.1 in subjects that are asymptomatic without signs or symptoms of impending visceral crisis SHOULD be confirmed by repeat scan to rule out "tumor flare" (pseudoprogression) related to immune response. In these subjects and per MD discretion, study therapy should be continued in these subjects until the repeat scan is performed approximately 4 weeks but no more than 6 weeks later. If PD is confirmed, subjects will be withdrawn from study. If tumor flare confirmed, subjects may continue therapy as per protocol. Subjects that have clear progressive disease as defined by RECIST 1.1 should be withdrawn from treatment and a repeat scan is not necessary.

**6.7.4.1 Evaluation of Best Overall Response** - The best overall responses for both RECIST 1.1 and irRECIST are defined as the best response achieved across all time points prior to progression (for example, a subject who has SD at first assessment, PR at second assessment, and PD on last assessment has a best overall response of PR). Please Note: In the case of SD, measurements must have met the SD criteria at least once after study entry at a minimum interval of 12 weeks from initiation of treatment.

The best overall response will be defined according to the following table:

Overall Response First Time Point	Overall Response Subsequent Time Point	BEST Overall Response
CR	CR	CR
CR	PR	SD, PD, or PR 
CR	SD	SD provided minimum criteria for SD duration met, otherwise, PD
CR	PD	SD provided minimum criteria for SD duration met, otherwise, PD
CR	NE 	SD provided minimum criteria for SD duration met, otherwise, NE 
PR	CR	PR
PR	PR	PR
PR	SD	SD
PR	PD	SD provided minimum criteria for SD duration met, otherwise, PD
PR	NE 	SD provided minimum criteria for SD duration met, otherwise, NE 
NE	NE 	NE 

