##### Pregnancy

Pregnancies and suspected pregnancies (including a positive pregnancy test regardless of age or disease state) of a female subject or a female partner of a male subject occurring while the subject is on study, or within the period stipulated for continued contraceptive use for WOCBP (5 months) and sexually active men (6 months) after the subject's last dose of study medication should be recorded as SAEs. The female subject is to be discontinued immediately from the study for a pregnancy event.

For Affiliate sites, the pregnancy, suspected pregnancy, or positive pregnancy test must be reported to the Multicenter Project Manager immediately (within 24 hours) at [contact] (primary route of submission) or [contact] (back-up)). The Multicenter Project Manager will then report the event to the Funding Source (see requirements below). The female subject or the female partner of a male subject should be referred to an obstetrician-gynecologist, preferably one experienced in reproductive toxicity for further evaluation and counseling.

The Investigator will follow the female subject or female partner of a male subject until completion of the pregnancy, and must document the outcome of the pregnancy (either normal or abnormal outcome) and report the condition of the fetus or newborn to the Multicenter Project Manager. If the outcome of the pregnancy was abnormal (e.g., spontaneous or therapeutic abortion), the Investigator should report the abnormal outcome as an AE. If the abnormal outcome meets any of the serious criteria, it must be reported as an SAE.

Note if the female subject or female partner of a male subject has received nivolumab, the investigator must immediately notify Worldwide Safety @BMS of this event via the Pregnancy Surveillance Form in accordance with SAE reporting procedures. The nivolumab IB notes that non-clinical safety findings of adverse pregnancy outcomes and infant losses in the absence of maternal toxicity have been reported. Findings in monkeys suggest a potential risk to human pregnancy if there is continued treatment with nivolumab during pregnancy.

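### Section 6.7.4 takes subjects with confirmed progression off study, while Sections 4.6 to 4.8 take them off protocol therapy only; read literally, it would cost survival data after progression

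*Combined protocol and SAP*

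**What the plan says.** The note in Section 6.7.4 deals with possible pseudoprogression. Asymptomatic subjects with RECIST 1.1 progression have a repeat scan, and then: "If PD is confirmed, subjects will be withdrawn from study". Two sentences later the note covers the remaining progressors: "Subjects that have clear progressive disease as defined by RECIST 1.1 should be withdrawn from treatment and a repeat scan is not necessary".

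Disposition is set out in Section 4. Section 4.6 lists progression, including progression confirmed by a repeat scan, under the lead-in "Subjects should continue protocol therapy as described until". Section 4.8 adds: "Subjects will be removed from protocol therapy and the PI notified when any of the criteria listed in section 4.6 apply". On survival, Section 4.7 says: "Subjects will be followed for up to 3 years after removal from study treatment for determination of OS", and extends post-treatment follow-up to all subjects. Footnote 3 of Section 6.1 and Section 6.4.4 schedule contacts every 90 days for up to 3 years or until death, recording survival status and later cancer treatments.

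Study withdrawal has its own section, 4.9, which begins "If a subject decides to withdraw from the study (and not just from protocol therapy". There, survival information depends on consent: "The subject should be asked if they are willing to allow for the abstraction of relevant information from their medical record".

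Section 2.4.2.4 defines OS from day 1 of treatment to death from any cause, with censoring of subjects who have not died by the analysis date. Section 8.4 estimates OS by Kaplan-Meier.

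**The concern.** The protocol uses study and protocol therapy as different terms with different consequences. A subject off therapy stays in survival follow-up for up to 3 years. A subject off study contributes later survival data only if they agree to record abstraction. Section 6.7.4 uses the study term for a group that 4.6 and 4.8 place in the therapy category.

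Section 9.5 asks sites to conduct the study exactly as the protocol describes, and under 9.4 each institution enters its own data. A site that recorded confirmed progression as study withdrawal would therefore have text to rely on. Its progressors would be lost to OS just when their risk of death is expected to rise, so the censoring would be informative and the OS curve would sit too high. Vital status not collected at the time may later be recoverable only with the subject's permission.

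**Working it through.** There is no plan figure to reproduce. Section 8.2 sizes the trial on response rate, and nothing is sized on OS. The check is a comparison of passages.

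| Section | Who | What happens |
|---|---|---|
| 6.7.4 note | progression confirmed on repeat scan | off study |
| 6.7.4 note | clear progression | off treatment |
| 4.6 with 4.8 | progression, including confirmed | off protocol therapy |
| 4.7; 6.1 footnote 3; 6.4.4 | subjects off treatment, no exception for progression | survival follow-up for up to 3 years |
| 4.9 | subject's own decision to leave the study | survival through record abstraction, if the subject agrees |
| 2.4.2.4 | subjects not dead at the analysis date | OS censored |

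1. Rows 1 and 3 cover the same subjects and give different dispositions.
2. Rows 1 and 2 give the more advanced exit to one kind of progressor and not the other, and no reason is stated.
3. Row 4 cannot be carried out for a subject handled under row 1 in its literal sense.
4. Row 6 contains no rule that censors at progression. It also cannot supply deaths that nobody collected. If contacts stop, the analysis would in practice have to censor at the last date known alive.

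**Illustration of the literal reading.** All inputs are assumptions; none is in the documents. Times are exponential. Median PFS is m = 4 or 6 months, median survival after progression is s = 6 or 9 months, and a share f = 5%, 10% or 20% of PFS events are deaths. Every progressor is lost at progression, so 1 − f, or 80 to 95%, are censored there.

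- Write a = ln 2/m and b = ln 2/s.
- True OS at 12 months = f·exp(−12a) + (1 − f)·H, where H = [a·exp(−12b) − b·exp(−12a)]/(a − b), or (1 + 12a)·exp(−12a) when a = b.
- Kaplan-Meier OS at 12 months with censoring at progression = exp(−12·f·a) = 2^(−12f/m).

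Example with m = 4, s = 6, f = 10%: H = (0.25 × 0.25 − 0.1667 × 0.125)/(0.25 − 0.1667) = 0.50. True OS = 0.10 × 0.125 + 0.90 × 0.50 = 0.46. Estimated OS = 2^(−0.3) = 0.81.

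Over all twelve combinations, true 12-month OS is 43 to 67% and the estimate is 66 to 93%. The smallest gap is 14 points (m = 4, s = 9, f = 20%: 52% against 66%). The largest is 42 points (m = 4, s = 6, f = 5%: 48% against 90%).

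This is an upper-end case. The challenged sentence covers only progressors confirmed by repeat scan, and the loss would occur only at sites that read it literally.

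**The case against.** The best reply is that the intended meaning is plain. Section 6.7.4 is about tumour measurement, and disposition belongs to 4.6 to 4.9. Section 4.9 speaks of a subject's decision, which a scan result is not, and 6.7.4 does not cite 4.9. Section 4.7 itself uses withdrawn loosely, for subjects off treatment for adverse events who are still followed. Collecting later cancer treatments in 6.4.4 makes most sense after progression. Off study therefore most naturally means off study treatment.

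Most of this stands, and it rules out a stronger reading: that 6.7.4 ends survival follow-up and so censors OS at progression. The documents do not support that. Sections 4.7, 6.1 and 6.4.4 continue follow-up, and 2.4.2.4 censors by vital status at the analysis date. Nor do they support a count of affected subjects. Taking 50 to 80% of the 56 evaluable subjects would give 28 to 45 (0.5 × 56 = 28; 0.8 × 56 = 44.8), but that share has no source. It also ignores that clear progressors need no repeat scan, and it requires every site to disregard 4.7.

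The reply does not remove the contradiction. The sentence in 6.7.4 is an instruction to sites, and the sections that protect OS are the ones it conflicts with.

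**Conclusion.** The inconsistency is real; its effect on OS is conditional. The plan as a whole intends survival follow-up after progression, and one operative sentence says otherwise for confirmed progressors. If sites follow that sentence, vital status is lost informatively and the Kaplan-Meier OS estimate is biased upward, on the assumption that mortality is higher after progression than before it. The documents do not allow the size to be derived; the illustration only shows that the bias would be large if the literal reading were applied universally.

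OS is a secondary, descriptive endpoint. The primary response rate and the two-stage decision rule in 8.2 are unaffected. PFS is also unaffected, because progression is itself the event.

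A lesser instance of the same wording is in the pregnancy part of 7.3.3: "The female subject is to be discontinued immediately from the study for a pregnancy event". That part also requires the subject to be followed until the pregnancy is completed, so the term cannot mean the end of all follow-up there either.

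**What to change.** In the 6.7.4 note, replace the off-study wording for confirmed progression with: removed from protocol therapy (4.8) and followed for survival per 4.7 and 6.4.4. Reconcile the pregnancy sentence in 7.3.3 with 4.7 to 4.9 so that it is clear follow-up continues.

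The cost is two phrases in the next amendment. No visits are added, because the contacts are already in 6.1 and 6.4.4. No treatment rule changes, because therapy stops after confirmed progression under either wording. If subjects have already been recorded as off study for confirmed progression, their survival follow-up status should be checked before the OS analysis.

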### 2.4.2 Secondary Endpoints

**2.4.2.1** The best overall responses for both RECIST 1.1 and irRECIST are defined as the best response achieved across all time points prior to progression (for example, a subject who has SD at first assessment, PR at second assessment, and PD on last assessment has a best overall response of PR). Please Note: In the case of SD, measurements must have met the SD criteria at least once after study entry at a minimum interval of 12 weeks from initiation of treatment.

**2.4.2.2** The immune-related response rate is defined as the percentage of subjects with unresectable refractory *KRAS/NRAS/BRAF* wild-type MSS mCRC who achieve a CR+PR by 12 weeks to panitumumab/nivolumab/ipilimumab or panitumumab/nivolumab therapy per irRECIST criteria. (See section 6.7.5.1)

**2.4.2.3** Assessment of immune-related PFS is defined as starting from the first day of treatment or Day 1 (D1) until the event of disease progression as defined by irRECIST, or death from any cause in subjects with unresectable refractory *KRAS/NRAS/BRAF* wild-type MSS mCRC (See section 6.7.5.1). Any subject that has not had a documented event at the time of analysis will be censored. Assessment of PFS (as defined by RECIST 1.1) is defined from D1 of treatment until the event of disease progression occurs or death from any cause in subjects with unresectable refractory *KRAS/NRAS/BRAF* wild-type MSS mCRC. Any

October 01,,  
2020

subject that has not had a documented event at the time of analysis will be censored.

- 2.4.2.4 OS is defined as the time from D1 of treatment until death from any cause. Any subject that has not died by the analysis date will be censored.
- 2.4.2.5 The duration of response as defined by RECIST 1.1 will be defined as the time elapsed from first scan documenting partial response or complete response until the event of disease progression occurs. Any subject that has not had a documented progression at the time of analysis will be censored. The duration of response as defined by irRECIST will be defined as the time elapsed from first scan documenting partial response or complete response until the event of disease progression occurs. Any subject that has not had a documented progression at the time of analysis will be censored.
- 2.4.2.6 Treatment-related adverse events will be assessed per NCI-CTCAE v4.03.

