**6.7.5 Other Efficacy Parameters (Immune Response Criteria)**

**6.7.5.1 Evaluation of Response by irRECIST**

Secondary objectives of this study involve assessment of ORR and PFS based in immune response criteria as outlined below (see Guidelines for the evaluation of immune therapy activity in solid tumors: immune-related response criteria. Wolchok JD et al. Clin Cancer Res 2009;15(23):7412-20, Nishino et al. Clin Cancer Res 19(14):3936-43, and Bohnsack O. et al., *Adaptation of the immune related response criteria: irRECIST*. Annals of Oncology (2014) 25 (suppl\_4): iv361-iv372. 10.1093/annonc/mdu342, 2014).

irRECIST criteria are based on irRC criteria (Wolchok et al) adapted for unidimensional measurement as outlined by Nishino et al. The adaptation described by Bohnsack et al. further aligns irRECIST to allow for assessment of

baseline non-target lesions and new non-measurable lesions and discusses the impact of those lesions on the overall tumor response assessment. The adaptation by Bohnsack et al. allows for evaluation of subjects with non-target disease only and subjects in the adjuvant setting (not applicable for this study in subjects with metastatic disease).

Overall response using the irRECIST is based on tumor burden as follows:

irCR	Complete disappearance of all lesions (whether measurable or not, and no new lesions) Lymph nodes must decrease to < 10 mm in short axis. Confirmation of response is not mandatory.
irPR	Decrease in tumor burden $\geq 30\%$ in TMTB relative to baseline confirmed by a consecutive assessment at least 4 weeks after first documentation, non-target lesions are irNN, and no equivocal progression of new non-measurable lesions.
irSD	Not meeting criteria for irCR, irPR, in absence of irPD
irPD	Increase in tumor burden $\geq 20\%$ increase and minimum 5 mm absolute increase in TMTB compared to nadir, or irPD for non-target or new non-measurable lesions confirmed by a repeat, consecutive assessment no less than 4 weeks from the date first documented
irNN	No target disease was identified at baseline and at follow-up the subject fails to meet criteria for irCR or irPD.

irNN = irNon-CR/Non-PD

TMTB = Total measurable tumor burden

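### irRECIST progression calls for a confirming scan that clear progressors need not have, so irRECIST PFS and duration of response are biased upward

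*Combined protocol and SAP*

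**What the plan says.** Objectives 2.2.3 and 2.2.5 ask for PFS and duration of response by both RECIST 1.1 and irRECIST. Section 2.4.2.3 runs irRECIST PFS from Day 1 "until the event of disease progression as defined by irRECIST, or death from any cause", and adds: "Any subject that has not had a documented event at the time of analysis will be censored". Section 2.4.2.5 ends irRECIST duration of response at progression only and censors subjects without a documented progression. Neither section gives a censoring date.

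The irPD row in section 6.7.5.1 has two limbs. One is a rise in total measurable tumor burden of at least 20% and 5 mm over nadir. The other concerns non-target or new non-measurable lesions. The row closes with the condition "confirmed by a repeat, consecutive assessment no less than 4 weeks from the date first documented".

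The note in section 6.7.4 says that RECIST 1.1 progression in asymptomatic subjects without impending visceral crisis "SHOULD be confirmed by repeat scan to rule out" pseudoprogression, at about 4 and no more than 6 weeks. It then says: "Subjects that have clear progressive disease as defined by RECIST 1.1 should be withdrawn from treatment and a repeat scan is not necessary". What makes progression clear is not defined.

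The Time and Events Table (6.1) lists tumor measurement before study and from Day 1 of Cycle 3 during treatment. It lists none at end of treatment or afterwards, and sections 6.4.1 to 6.4.4 add none. Section 8.4 specifies Kaplan-Meier estimation and has no rule for irPD that was never confirmed.

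**The concern.** The irRECIST endpoints need a second scan before progression counts, while section 6.7.4 releases one group of progressors from that scan. Nothing in the endpoint definitions or in section 8.4 says what happens to that group. Whether a progression becomes an irRECIST event then depends on whether a site chose to rescan. The group least likely to be rescanned, namely subjects with symptoms or with progression judged clear, is unlikely to be a random sample of progressors, so any censoring is probably informative.

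At stake is the comparison between the two criteria. RECIST 1.1 and irRECIST PFS will be reported together. A longer irRECIST curve would naturally be taken as evidence of pseudoprogression, when part of the gap could come from the rescan rule alone.

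**Working it through.** **The plan's own figure.** The documents state no number for irRECIST PFS. The only sized endpoint is ORR (section 8.2): stop at 6 or fewer responders of 32, success at 17 or more of 56, null 22%, alternative 35%. An exact two-stage binomial calculation gives alpha 0.0903, power 0.8012 and probability 0.424 of meeting the stage 1 futility criterion under the null. A search returns the same design as minimax, so the stated design reproduces. It has no bearing on this point beyond supplying N = 56.

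**Tracing one subject.** A subject is judged to have clear RECIST 1.1 progression, stops treatment and has no later scan.

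1. RECIST 1.1 PFS: event at that scan.
2. irRECIST PFS: confirmation is missing, so there is no progression date. The event is death if captured; otherwise the subject is censored at an unstated date.
3. irRECIST duration of response, if the subject had responded: no progression date and no death event, so censored even after death.

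**Direction.** Compare with counting the progression at its first date. Moving an event to a later death cannot lower the Kaplan-Meier curve, and neither can turning an event into a censoring at the same time. The bias is therefore upward either way.

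**Illustration 1 (assumed counts).** 56 at risk, 20 progress at the first scan, confirmed events are dated at that scan, and there are no earlier events or censoring. The step is S = 1 − events/56.

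- All 20 counted: 1 − 20/56 = 36/56 = 64%.
- 5 unconfirmed: 1 − 15/56 = 41/56 = 73%.
- 10 unconfirmed: 1 − 10/56 = 46/56 = 82%.

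The step is the same whether the unconfirmed subjects are censored there or stay at risk until death.

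**Illustration 2 (assumed exponential times).** Median time to first progression m is 4 or 6 months, median survival after progression is 6 or 10 months, and a share f of progressors, chosen at random, is unconfirmed. If they are censored at the scan, the progression hazard is multiplied by (1 − f), so the median becomes m/(1 − f); for example 4/0.75 = 5.3 and 6/0.75 = 8.0. The run-to-death medians come from 200,000 simulated subjects per setting.

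| True median | f | Censored at scan | Run to death |
|---|---|---|---|
| 4.0 | 10% | 4.4 | 4.5–4.6 |
| 4.0 | 25% | 5.3 | 5.4–5.7 |
| 4.0 | 50% | 8.0 | 7.4–8.5 |
| 6.0 | 10% | 6.7 | 6.7–6.8 |
| 6.0 | 25% | 8.0 | 7.7–8.2 |
| 6.0 | 50% | about 12 | 9.9–11.5 |

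At f = 25% the median rises by 1.3 (5.3 − 4.0) to 2.2 (8.2 − 6.0) months. Six-month PFS goes from 0.35 to 0.46–0.48, or from 0.50 to 0.59–0.60, a gain of 9 to 13 points. None of these inputs is in the documents.

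**Repeat-scan timing.** Section 4.6 says "treatment should continue until progression is confirmed by repeat scan approximately 6 weeks later to rule out pseudoprogression based on investigator discretion". Section 6.7.4 sets about 4 weeks, no more than 6. Section 6.7.5.1 sets at least 4. A scan a day or two short of 4 weeks can satisfy section 6.7.4 and still fail to confirm irPD.

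**The case against.** Several points on the other side stand and limit the finding.

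- **Death is an irRECIST PFS event.** A reader might infer that clear progressors never have an event. Section 2.4.2.3 counts death from any cause and section 4.7 follows survival for up to 3 years after treatment. For PFS the event is usually delayed, not lost. If unconfirmed subjects are close to death, the delay is short. This does not help duration of response.
- **The confirmation phrase may be narrower.** The row reads "or irPD for non-target or new non-measurable lesions confirmed by a repeat, consecutive assessment", so confirmation could attach to that limb only. Target-burden progression would then count at once, and the gap would be confined to non-target and new non-measurable lesions. Applying it to all irPD is the more natural reading, since the irPR row also requires confirmation, but the text does not settle it. Two analysts could draw different curves from the same data.
- **A rescan is optional, not barred.** Some clear progressors may be confirmed. A reader might also infer that equivocal scans are repeated and obvious ones are not. The stated trigger for a rescan is absence of symptoms, not an equivocal image.
- **Cited criteria papers.** Section 6.7.5.1 cites published irRECIST sources that may cover irPD with no later scan. That cannot be checked from the documents, and the plan does not say it adopts such a rule.
- **OS.** Section 6.7.4 also says "If PD is confirmed, subjects will be withdrawn from study". A reader might infer that survival follow-up ends there. Section 4.7 says all subjects are followed after removal from treatment, sections 6.1 (footnote 3) and 6.4.4 schedule survival contacts, and section 4.9 treats leaving the study as separate from leaving therapy. The wording is loose, but loss of OS data is not supported.

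What remains is that the rules conflict for clear progressors who are not rescanned, and no analysis rule resolves the conflict.

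**Conclusion.** The concern holds for irRECIST PFS and, more sharply, for irRECIST duration of response. Followed as written, the plan leaves an unrescanned clear progressor without an irRECIST progression date, on the natural reading for any irPD and on the narrower reading for non-target or new non-measurable lesions. The direction of bias is upward. Its size cannot be derived, because the documents give no share of clear progressors, no PFS median and no survival after progression. The 73% to 82% against 64%, and the simulated medians, show what assumed shares would do; they are not forecasts. Both endpoints are secondary and are estimated without a stated test. Primary ORR, RECIST 1.1 PFS and OS are not affected. The wording should be corrected before the irRECIST analyses are run.

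**What to change.** In sections 2.4.2.3, 2.4.2.5 and 6.7.5.1:

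1. State which limbs of irPD need confirmation.
2. State that irPD with no later assessment (treatment stopped for clear progression, new anticancer therapy, or death) counts as irPD on the date first documented, and that only irPD contradicted by a later scan at least 4 weeks after is reset.
3. Define the censoring date for both endpoints.

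If the sponsor prefers another convention for unconfirmed irPD, it should be written down and paired with a sensitivity analysis using the rule in item 2.

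Separately, reconcile the repeat-scan timing in sections 4.6, 6.7.4 and 6.7.5.1, and the withdrawal wording in section 6.7.4 with sections 4.7 and 4.9. No view is given here on which clinical rule is right.

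The analysis change costs endpoint wording only, with no added scans or subjects. The price is somewhat less favourable irRECIST PFS and duration-of-response medians, and any pseudoprogression that was never rescanned will count as progression.
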